6.10 Discontinuation and Withdrawal Criteria

6.10.1 Discontinuation of Treatment

Patients may voluntarily discontinue from treatment for any reason at any time. If a patient decides to discontinue from treatment, the Investigator must make every effort to determine the primary reason for this decision. The reason for discontinuation should be recorded in the patient's chart and on the appropriate eCRF pages.

Patients who discontinue IMP treatment during the Double-Blind Treatment Period should NOT be considered withdrawn from the trial. Every effort will be made to keep patients who discontinue IMP treatment in the trial. They should return for the assessments indicated in Table 3, up to Week 53. A PK sample and an immunogenicity sample should be collected at least 5 weeks after the last dose of IMP.

If the patients fail to return for these assessments for unknown reasons, every effort (e.g., telephone, email, letter) should be made to contact them. Patients who discontinue IMP treatment during the Extension Period should be asked to complete an End-of-Treatment Visit as soon as possible after the last dose of IMP, and a Safety Follow-Up Visit at least 5 weeks after last dose of IMP.

The Investigator should discontinue a patient's IMP treatment if he/she believes that continuation would be detrimental to the patient's well-being or if the patient experiences an intercurrent illness that compromises the patient's ability to fulfil protocol requirements. The Investigator should contact the Medical Monitor before a patient is discontinued from IMP treatment.

IMP treatment must be discontinued under the following circumstances:

- Development of decreased kidney function as defined by $\text{eGFR} < 25 \text{ mL/min/1.73 m}^2$.
- Pregnancy (see [Section 7.6.1.1](#)).
- Any protocol deviation (including prohibited concomitant therapy, see [Section 6.9.3](#)) that results in a significant risk to the patient's safety or that will interfere with the assessment of the efficacy endpoints of this trial, including significant non-compliance with the trial protocol and procedures.

In addition to the general treatment discontinuation criteria, the toxicity-related criteria listed below will also require IMP treatment discontinuation. The final decision to discontinue IMP treatment is up to the judgment of the Investigator.

Hepatic-related Discontinuation Criteria

- ALT or AST levels $> 8 \times$ upper limit of normal.

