- ALT or AST levels $> 5 \times$ upper limit of normal for more than 2 weeks.
- Clinically significant and prolonged symptoms of reduced hepatic function, e.g., appearance of chronic fatigue, nausea, vomiting, right upper quadrant pain or tenderness, itchy skin, or swelling of legs and ankles.
- The patient is diagnosed with liver cirrhosis of Child-Pugh class C.
- The patient is diagnosed with hepatic decompensation with European foundation for the study of CLIF-C ACLF score 2 or 3 ([40](#)).

Re-challenge is not recommended when IMP treatment is discontinued due to the above criteria.

For details on follow-up of potential drug-induced liver injury cases, refer to [Section 17.1.1](#), Appendix 1.

Cyst-related Discontinuation Criteria

- Progression of extrahepatic cysts that, in the Investigator's opinion, may prevent the patient from safely participating in the trial.

Cardiac-related Discontinuation Criteria

- $\text{QT/QTcF} \geq 501 \text{ msec}$ or $> 60 \text{ msec}$ increase from baseline (average of triplicate ECG) after repeated triplicate measurement and as confirmed by central ECG reader.
- Torsades de Pointes
- Polymorphic ventricular tachycardia
- Signs/symptoms of serious arrhythmia
- Use of QT-prolonging medication with a known risk of Torsade de Pointes.
- Hypokalemia ($< 3.5 \text{ mmol/L}$) or hypomagnesemia ($< 0.7 \text{ mmol/L}$), or clinically significant hypocalcemia confirmed by repeated testing that is either a new finding or accompanied by vomiting or diarrhea and not corrected by treatment.

For details on QT prolongation management, refer to [Section 17.1.2](#) Appendix 1.

Hyperglycemia-related Discontinuation Criteria

- Patients with hemoglobin A1c $\geq 10\%$ at 3 consecutive visits (including unscheduled visits) despite prior appropriate management.

General Toxicity Discontinuation Criteria

- For ADRs with CTCAE grade 3, treatment should be delayed until the ADR resolves or improves to CTCAE grade ≤ 2 . If the ADR is expected to re-occur upon re-challenge, consider discontinuing IMP permanently. If ADR does not resolve or improve to CTCAE grade ≤ 2 (mild or moderate) within 28 days, IMP must be permanently discontinued.
- For AEs with CTCAE grade ≥ 4 regardless of relatedness to the IMP, treatment will be discontinued until further review.

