7.6.6 Electrocardiogram

ECGs will be recorded and readings will be transmitted to a selected ECG central laboratory for analysis. Triplicate 12-lead ECG (3 ECG recordings at approximately 2-minute intervals) will be performed at each scheduled time point. The combined QTcF values from triplicate ECGs will be averaged to provide a single value for each patient. ECGs will be recorded at screening and at the time points outlined in [Table 3](#).

ECGs will be recorded after the patient has been resting in a supine position for at least 10 minutes. All ECGs should be recorded with the patient in the same physical position. ECGs will be recorded after vital signs and before blood samples for PK and clinical safety laboratory assessments.

The ECG assessments pre-dose and at the 24-hour time point have been selected to coincide with trough concentrations and near C_{max} of octreotide for CAM2029, based on PK results from trial HS-11-411. If at any visit QTcF ≥ 481 msec is observed, the procedures for QT-prolongation management described in [Section 17.1.2](#), Appendix 1 must be considered.

All ECG assessments will initially be assessed by the Investigator/qualified physician for any findings that require immediate medical attention. All ECGs will also be read by an ECG central reader. The clinical significance of any ECG findings will be determined by the Investigator, including after the central reading result is available. However, only ECG results provided by the central reader will be recorded in the clinical database.

Clinically significant abnormalities that are known at the time of signing the ICF should be reported on the Medical History eCRF page. Clinically significant findings must be discussed with the Sponsor before enrolling the patient in the trial. New or worsened clinically significant findings occurring after signing of the ICF must be recorded on the AE page of the eCRF.

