17.1.2 Specific Management Recommendations for Cases of QTcF Prolongation

Table 5: Dose interruptions for QTcF prolongation

Severity	Dose adjustment and management recommendation
For all grades	
Check the quality of the ECG and the QT value and repeat if needed. Analyze serum electrolytes (potassium, calcium, phosphorus, magnesium). If electrolytes are significantly outside of normal range, correct with supplements or appropriate therapy as soon as possible, and repeat electrolyte analyses until documented as normal.
 
Review concomitant medication usage for the potential to prolong the QT interval.
 
Check compliance with correct dose and administration of IMP.
 
Consider collecting a time-matched PK sample; record date and time of last IMP intake.

Grade 1
 
Average QTcF: Males: 450 msec to 480 msec Females: 470 msec to 480 msec
	No dose interruption recommended.

Grade 2
 
Average QTcF: 481 msec to 500 msec
	
Pause IMP.
 
Perform repeated triplicate ECGs approximately 1 hour after the first QTcF of ≥ 481 msec.
 
If QTcF < 481 msec, restart IMP.
 
If QTcF remains ≥ 481 msec, repeat ECG as clinically indicated until the QTcF returns to < 481 msec. Restart IMP.
 
If QTcF ≥ 481 msec remains or recurs, consider discontinuing IMP.
 
Repeat ECGs 7 days and 14 days after dose resumption (then as clinically indicated) for any patient who had therapy interrupted due to QTcF ≥ 481 msec.

Grade 3
 
Average QTcF: ≥ 501 msec or > 60 msec change from baseline
 
or
 
Grade 4
 
Torsades de pointes or polymorphic ventricular tachycardia, or signs/symptoms of serious arrhythmia
	
Perform repeated triplicate ECGs within 1 hour of the first QTcF of ≥ 501 msec or > 60 msec change from baseline.
 
If QTcF remains ≥ 501 msec or if the change from baseline remains > 60 msec, discontinue IMP.
 
Transmit ECG immediately and confirm prolongation/abnormalities with central assessment.
 
Obtain local cardiologist (or qualified specialist) consultation and repeat cardiac monitoring as indicated until the QTcF returns to ≤ 500 msec.
 
Repeat ECG as clinically indicated until the QTcF returns to < 481 msec.

ECG: electrocardiogram; IMP: investigational medicinal product; PK: pharmacokinetic; QTcF: QTc interval corrected by Fridericia's formula

SPONSOR PROTOCOL SIGNATURE PAGE

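### Table 5's Grade 2 restart lines test only absolute QTcF, so they overlap, with no rule of precedence, with the criterion to discontinue on a confirmed rise of more than 60 msec

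*Protocol*

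**What the plan says.** Table 5 in Protocol Section 17.1.2 grades QTcF prolongation and attaches an action to each grade.

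- **Grade 1** is an absolute QTcF of up to 480 msec. No interruption is recommended.
- **Grade 2** is an absolute QTcF of 481 to 500 msec. IMP is paused and triplicate ECGs are repeated after about 1 hour. Three lines follow. The first is "If QTcF < 481 msec, restart IMP". The second covers a repeat that stays at 481 msec or above: "repeat ECG as clinically indicated until the QTcF returns to < 481 msec. Restart IMP". The third says that if such a value "remains or recurs, consider discontinuing IMP". None of them mentions change from baseline.
- **Grade 3** is 501 msec or more, or a change of more than 60 msec. The ECG is repeated within 1 hour, and IMP is discontinued if QTcF stays at 501 msec or above "or if the change from baseline remains" above 60 msec.

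Section 6.10.1 introduces its cardiac and other lists by saying that "the toxicity-related criteria listed below will also require IMP treatment discontinuation". The cardiac list includes a rise of more than 60 msec "after repeated triplicate measurement and as confirmed by central ECG reader", with no condition on the absolute value. It also says: "The final decision to discontinue IMP treatment is up to the judgment of the Investigator".

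Section 7.6.6 states that if a QTcF of at least 481 msec "is observed, the procedures for QT-prolongation management described in" Section 17.1.2 must be considered. The rise from baseline is not part of that trigger.

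**The concern.** The Grade 2 and Grade 3 rows are not mutually exclusive, and their actions can oppose each other. A patient with a low baseline can have a reading inside the Grade 2 band that is also more than 60 msec above baseline. The Grade 2 row then gives an affirmative instruction to restart on the absolute value alone, while the Grade 3 row says to stop if the rise persists. No sentence in the table sets precedence.

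Sections 6.2.3, 6.10.1 and 7.6.6 all send sites to this appendix. On visit days assessments precede dosing (Table 3 footnote), and the investigator reads the ECG before the central result arrives (Section 7.6.6), so the dosing decision may be taken on the spot from this table. At stake is an avoidable dose of a long-acting depot, which cannot be withdrawn, in a patient who meets the protocol's own criterion for discontinuation.

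**Working it through.** The plan states no figure to reproduce, so the check sets the cut-offs against each other. Values are in whole msec, so a rise of more than 60 means at least 61.

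**Inputs.** Grade 2 band 481–500; restart below 481 (at most 480); Grade 3 at 501 or more, or a rise of at least 61 (all Table 5). Screening excludes only QTcF above 450 (males) or above 470 (females), with no lower limit (Section 5.3, criterion 12.c.iii).

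**1. When does a Grade 2 reading also meet Grade 3?** The condition is reading − baseline ≥ 61.

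- The whole band overlaps if 481 − baseline ≥ 61, so baseline ≤ 420.
- Some of the band overlaps if 500 − baseline ≥ 61, so baseline ≤ 439.
- Between 421 and 439 the number of overlapping values is 500 − (baseline + 61) + 1 = 440 − baseline. At 430 this is 10 of 20 values (491–500); at 439 it is 1.
- At 440 or above there is no overlap.

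Screening admits all the baselines concerned.

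**2. First restart line.** A clash needs a repeat ≤ 480 with a rise still ≥ 61, so baseline ≤ 480 − 61 = 419. Example: baseline 410, first reading 485 (+75), repeat 475 (+65). Grade 2 says restart because 475 is below 481. Grade 3 says discontinue because +65 is above 60. At this baseline the clashing repeats are 471–480.

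In every such case the first reading was already Grade 3, since 481 − 419 = 62. Enumerating baselines 350–470, first readings 481–500 and repeats 380–480 gave the same limit of 419, and no clash in a patient who met Grade 2 only.

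**3. Second restart line.** A clash needs a repeat of 481–500 with a confirmed rise ≥ 61, so baseline ≤ 500 − 61 = 439. Example: baseline 430, first reading and repeat both 492 (+62), later 478 (+48). Grade 2 says keep repeating and restart at 478, with discontinuation only to be considered. Grade 3 and, with central confirmation, Section 6.10.1 call for stopping at the confirmed +62.

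**4. Grade 1 row and Section 7.6.6 trigger.** A rise ≥ 61 with QTcF ≤ 480 again needs baseline ≤ 419. Example: 380 to 445 (+65) is Grade 3 by the change criterion but lies below the 481 msec trigger.

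**5. Added exposure from one mistaken dose.** SAP Section 5.8.1 counts exposure as last dose minus first dose plus 5 half-lives, and 5 × 10.6 = 53 days. That tail already runs from the previous dose. An active dose given g days after the previous active one (g up to 53) moves the end of the tail from day 53 to day g + 53, an extension of g days.

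- Weekly active dosing on schedule: 60 − 53 = 7 days.
- 2-weekly active dosing on schedule: 67 − 53 = 14 days.
- A placebo injection adds no octreotide.
- The extension nears 53 days only if the gap since the last active dose does.

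**The case against.** The strongest reply is that Table 5 is a severity ladder. In the first-line clashes the patient is Grade 3 at the first reading, and in the second-line clashes by the time the rise is confirmed. A clinician who applies the highest grade met would follow the Grade 3 row. Section 6.10.1 independently lists the confirmed rise among its discontinuation criteria, and the appendix presents itself as recommendations. There are further safeguards: dose delays should preferably be discussed with the Medical Monitor (Section 6.2.3), every ECG is read centrally (Section 7.6.6), the DMC reviews the listed events while active, and Grade 2 requires ECGs 7 and 14 days after dosing resumes. All of this stands and limits the risk. It does not remove the inconsistency, because the table never states the highest-grade convention and one of its rows tells the site to restart.

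Three stronger readings are tempting, and the documents do not support them.

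- **That rises of more than 60 msec below 481 msec go unmanaged.** Section 7.6.6 does not say that its trigger is the only route to Table 5. Section 6.10.1 covers the rise and refers to Section 17.1.2, and Section 6.2.3 points there for QTcF prolongation without a threshold. The trigger is narrower than the stopping criterion, but the criterion is not missing.
- **That one mistaken dose adds 53 days of exposure.** The 53-day tail is already running from the previous dose, as step 5 of the working shows.
- **That the protocol as a whole directs re-dosing.** Taken together it points to stopping, with the final decision left to the investigator.

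**Conclusion.** The point holds as a limited internal inconsistency in safety guidance. The Grade 2 and Grade 3 rows overlap at baselines up to 439 msec. The first restart line clashes with the discontinuation criterion at baselines up to 419 msec and the second at baselines up to 439 msec. The Section 7.6.6 trigger is narrower than Section 6.10.1 at baselines up to 419 msec.

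These limits follow from the protocol's own cut-offs in whole msec and need no assumed distribution. The documents give neither the distribution of baseline QTcF nor the frequency of rises above 60 msec, so the number of patients affected cannot be estimated. The exposure figures of about 7 and 14 days assume an active dose given on schedule and the SAP's half-life. Sample size, power and the primary analysis are unaffected. It should be fixed because a written line can direct a wrong re-dose and the correction costs little.

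**What to change.** 1. In Table 5, define Grade 2 as QTcF 481–500 msec and change from baseline ≤60 msec. Make both restart lines conditional on QTcF <481 msec and no confirmed change from baseline >60 msec.
2. In the Grade 3 row, add a pause of IMP pending the repeat ECG. State that if the repeat is ≤500 msec with a change ≤60 msec, the Grade 2 restart and 7- and 14-day ECG steps apply.
3. In the Grade 1 row, note that a rise >60 msec is managed as Grade 3.
4. In Section 7.6.6, widen the trigger to QTcF ≥481 msec or an increase from baseline >60 msec, to match Section 6.10.1.

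A single sentence saying that the highest grade governs would be shorter but is not enough. The Grade 3 row has no pause, restart or follow-up ECG instruction, so a first reading of 485 msec (+75) would lose its explicit pause while the repeat is awaited. With items 1 and 2, baseline 410 with 485 then 475 (+65) leads to discontinuation, while 485 then 465 (+55) leads to restart with follow-up ECGs.

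The cost is minor wording in one table and one section, a site memo, and an occasional unscheduled repeat ECG that Table 5 already calls for.

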FCS	Fully conditional specification
FDA	US Food and Drug Administration
GCP	Good Clinical Practice
GI	Gastrointestinal
htTLV	Height-adjusted total liver volume
htTKV	Height-adjusted total kidney volume
IB	Investigator's Brochure
ICF	Informed consent form
ICH	International Council for Harmonisation
IEC	Independent Ethics Committee
████	████████████████████
IMP	Investigational medicinal product
IR	Immediate release
IRB	Institutional Review Board
ITT	Intention-to-treat
LAR	Long-acting release
LLT	Lowest level term
LOCF	Last observation carried forward
LS	Least square
MAR	Missing at random
MedDRA	Medical Dictionary for Regulatory Activities
MI	Multiple imputation
MMRM	Mixed-effects model repeated measures
MRI	Magnetic resonance imaging
NCI	National Cancer Institute
OC	Observed cases
PC1	Polycystin-1
PC2	Polycystin-2
PD	Pharmacodynamic(s)
PGI-C	Patient Global Impression of Change
PGI-S	Patient Global Impression of Severity
PK	Pharmacokinetic(s)
PLD	Polycystic liver disease

PLD-I	Polycystic Liver Disease Impact
PLD-S	Polycystic Liver Disease Symptoms
PLD-Q	Polycystic Liver Disease Questionnaire
PPS	Per protocol analysis set
PQC	Product Quality Complaint
PRO	Patient-reported outcome
PT	Preferred term
Q1W	Once weekly
Q2W	Every 2 weeks
QTcF	QTc interval corrected by Fridericia's formula
SAE	Serious adverse event
SAF	Safety analysis set
SAP	Statistical analysis plan
SC	Subcutaneous
SD	Standard deviation
SF-36	Short Form-36
SOC	System organ class
SRL	Somatostatin receptor ligand
TEAE	Treatment-emergent adverse event
TESAE	Treatment-emergent serious adverse event
TLF	Table, Listing, and Figure
TLV	Total liver volume
US	United States
WHO-DD	World Health Organization Drug Dictionary

DEFINITION OF TERMS

CAM2029 Q1W	CAM2029 10 mg once weekly
CAM2029 Q2W	CAM2029 10 mg once every 2 weeks (weekly alternation with placebo)

CAM2029	The 2 CAM2029 treatment groups together
Placebo	Placebo once weekly
Overall	CAM2029 and Placebo together

1 STATISTICAL ANALYSIS PLAN STATEMENTS

Scope

This SAP will cover the planned analyses and reporting of the results from the double-blind treatment period of HS-20-677. A separate analysis plan will be written to cover the extension period following the double-blind period.

2 INTRODUCTION

The protocol for Trial HS-20-677 describes the general approach to analysis of data from the trial. This SAP provides additional details needed to complete such an analysis. Table, Listing, and Figure (TLF) shells are provided in a separate document.

This SAP will govern the efficacy, safety analysis, and descriptive summaries of PK data from this trial, see [Section 1](#). The details of PK parameter derivations are outside the scope of this analysis plan and will be covered in a separate analysis plan, if applicable. The SAP may be modified until the time of database lock and treatment unblinding for the primary analysis. Any deviations from the analysis plan, including deviations made after treatment unblinding, will be documented as such in the trial report.

Changes to the protocol-planned analyses are described in [Section 5.15](#).

This SAP is written based on version 8.0 of clinical trial protocol HS-20-677 (dated 29-Jan-2025).

2.1 Objectives, Endpoints, and Estimands

Table 1: Primary objective, endpoint and estimand

Primary Objective	Primary Endpoint / Estimand

To evaluate the treatment effect of CAM2029 compared to placebo on liver volume in patients with PLD	
Endpoint: Change from baseline to Week 53 in htTLV as determined by MRI volumetry
 
Estimand: The primary estimand of interest is the mean change from baseline to Week 53 in htTLV comparing 2 doses of CAM2029 to placebo in patients with PLD, had no patients started treatment with alternative SRL or undergone any therapeutic intervention with the intention to reduce the liver size, and is defined by the following attributes:
 
Treatment condition: The primary treatment condition of interest is the average effect of:
The CAM2029 treatment (10 mg once weekly and 10 mg every 2 weeks) vs placebo treatment 
Thereafter, the treatment conditions of interest are the effects of:
 
CAM2029 10 mg once weekly vs placeboCAM2029 10 mg every 2 weeks vs placebo 
Target population: The population targeted by the clinical question is defined as patients in the ITT analysis set as defined by the inclusion/exclusion criteria in the trial protocol.Variable (endpoint): The variable addressing the primary clinical question is change from baseline in htTLV as assessed at Week 53.Handling of intercurrent events: Intercurrent events will be handled through a combination of a treatment policy strategy and a hypothetical strategy depending on other treatment received and therapeutic interventions conducted while still in the trial:

Primary Objective	Primary Endpoint / Estimand
	
• IMP treatment discontinuation: Patients who discontinue treatment with IMP and do not receive another SRL or have any therapeutic interventions with the intention to reduce the liver size while still in the trial will be analyzed by the treatment policy strategy, i.e., observations collected after IMP discontinuation will be included in the analysis as they were collected. For patients who discontinue treatment with IMP and start receiving another SRL or have any therapeutic intervention with the intention to reduce the liver size while still in the trial, only observations collected prior to the start of the SRL and the therapeutic intervention will be included in the analyses. Observations collected after the start of the SRL and the therapeutic intervention will be handled using the method described below.• Use of another SRL (see Appendix 12): Patients who receive an SRL other than the trial IMP while still in the trial, will be handled according to a hypothetical strategy. That is, any measurements of htTLV following the start of any other SRL administration will be set to missing and not used in the analysis. This hypothetical strategy is motivated by the fact that no approved alternative SRL treatment for PLD is available in most countries.• Therapeutic interventions: Patients undergoing therapeutic intervention with the intention to reduce the liver size while still in the trial will be handled according to a hypothetical strategy. That is, measurements of htTLV following this intercurrent event will be set to missing and not used in the analysis. This strategy is motivated by the fact that such interventions may directly impact the primary endpoint without being related to the effect of the IMP.• Missing values: If the htTLV cannot be determined at Week 53, either due to start of another SRL treatment or after a therapeutic intervention with the intention to reduce the liver size after IMP discontinuation or values are missing for other reasons, missing values will be imputed using the MI method described in the Section 5.3.1 and Section 5.9.2.2. 
5. Population-level summary for comparison between treatment conditions: Mean change from baseline to Week 53 in htTLV

Table 2: Key Secondary objective, endpoint and estimand

[figure not shown]
[figure not shown]
Key Secondary Objective	Key Secondary Endpoint / Estimand

To evaluate the treatment effect of CAM2029 compared to placebo on patient-reported PLD-related symptoms	Endpoint: Change from baseline to Week 53 in the PLD-S measure score 

Table 3: Secondary objectives, endpoints and estimands

Secondary Objective	Secondary Endpoint / Estimand

To evaluate the treatment effect of CAM2029 on liver volume over time in patients with PLD	Endpoint: Change from baseline in htTLV as determined by MRI volumetry 

To evaluate the treatment effect of CAM2029 on patient-reported PLD-related symptoms over time	Endpoint: Change from baseline in the PLD-S measure score 

Secondary Objective	Secondary Endpoint / Estimand

To evaluate the treatment effect of CAM2029 over time on kidney volume in patients with presence of kidney cysts	Endpoint: Change from baseline in htTKV as measured by MRI volumetry

Secondary Objective	Secondary Endpoint / Estimand

To evaluate treatment effect of CAM2029 over time on total liver cyst volume	Endpoint: Change from baseline in total liver cyst volume determined by MRI volumetry

Secondary Objective	Secondary Endpoint / Estimand

To evaluate the treatment effect of CAM2029 over time on renal function in patients with presence of kidney cysts	Endpoint: Change from baseline in eGFR, assessed by the CKD-EPI cystatin C equation using serum concentrations of creatinine and cystatin C

To evaluate the treatment effect of CAM2029 over time on patient-reported PLD-related impact on functioning and well-being	Endpoint: Change from baseline in the PLD-I measure score

To evaluate the treatment effect of CAM2029 over time on PLD-related symptoms	Endpoints: 
Change from baseline in the CGI-S scoreChange from baseline in the PGI-S scoreChange from baseline in the PGI-C score

Secondary Objective	Secondary Endpoint / Estimand

To evaluate the treatment effect of CAM2029 over time on functioning and well-being	

To evaluate the treatment effect of CAM2029 over time on PLD-related symptoms	Endpoint: Change from baseline in the PLD-Q score

To evaluate the safety and tolerability of CAM2029	Endpoints: 
Incidence of AEsChanges from baseline in laboratory values, vital signs and ECG readings

To assess the PK of octreotide after administration of CAM2029	Endpoint: Octreotide plasma concentrations over time

Table 4: Exploratory objectives, and endpoints

Exploratory Objectives	Exploratory Endpoints

